4.3.2. Secondary Analyses

Body Weight (kg):

Descriptive statistics for the actual, change and percent change from baseline in body weight (kg) will be presented for patients of the FAS for all visits by subgroup of RGDO and overall.

Daily Hunger Scores:

Descriptive statistics for the actual and change from baseline in the weekly average of the daily hunger score for non-cognitively impaired patients in the FAS will be provided for all weeks by subgroup of RGDO. Descriptive statistics for the actual and change from baseline in the weekly average of the daily hunger score for patients in the FAS will be provided for the ~3 month analysis endpoint (identified as per handling approach of primary efficacy endpoint) by RGDO for exploratory purposes.

Prior to summarization, daily hunger scores for each of the 3 hunger assessments for patients ≥ 12 years of age will be averaged separately by week. For patients < 12 years of age, there is only one daily hunger assessment to be averaged by week. For a week of hunger scores to be considered evaluable, scores need to be recorded and available for analysis on at least 1 of 7 days to provide sufficient data to determine mean values. If sufficient data is not available to determine mean values, mean hunger score for that week will be considered missing.

Descriptive statistics for the actual and change from baseline in the weekly average of the daily hunger score for patients in the FAS will also be provided for all weeks by subgroup of RGDO and where scores need to be recorded and available for analysis on at least 3 of 7 days. If sufficient data is not available to determine mean values, mean hunger score for that week will be considered missing.

Global Hunger Scores:

Global Hunger Scores will be summarized by visit by subgroup of RGDO. Shift from baseline in global hunger score for patients in the FAS will be provided by subgroup of RGDO by visit.

Waist Circumference (cm):

Descriptive statistics for the actual and change from baseline in waist circumference (cm) for patients in the FAS will be provided for all visits by subgroup of RGDO.

[REDACTED]

A series of black horizontal bars of varying lengths, likely representing data or text that has been redacted or obscured. The bars are arranged vertically and appear to be of different widths, suggesting they represent different pieces of information or different lines of text. The black bars are set against a white background.

The figure displays a 10x10 grid of black and white bars, representing a sparse matrix. The non-zero elements are highlighted in white. The matrix features a prominent main diagonal of white bars. There are several off-diagonal patterns: a vertical column of white bars at the second position from the left; a horizontal row of white bars at the second position from the top; a diagonal line of white bars extending from the fourth position on the left to the eighth position on the top; and a diagonal line of white bars extending from the eighth position on the left to the fourth position on the top. The remaining elements in the grid are black.

A 10x10 grid of black bars on a white background. The bars are arranged in a pattern where each row has a different number of bars. The first row has 1 bar, the second has 2, the third has 3, and so on, up to the tenth row which has 10 bars. The bars are of uniform width and are separated by small gaps.

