For pre-amendment 9 patients, the treatment phase of the study will begin with an initial period of dose titration in 0.5 mg increments and lasting between 2 and 12 weeks. The dosing will range from as brief as a single dose step at either 1.0 mg for adults or 0.5 mg for adolescent (ages 12 – 18 years) patients, to as many as 5 (adults) or 6 (adolescents) dose steps to reach 3.0 mg once-daily. The highest potential dose allowed in dose titration, however, is expected to be 2.5 mg, with the option to progress further to 3.0 mg if there is a lack of response at 2.5 mg. Thus, each patient will have his/her dose individualized depending on the number of dosing increments administered, where each individual patient's therapeutic dose will be established by upwards dose titration in 2-week intervals. Thereafter, patients will continue on active treatment at their optimal therapeutic dose for an additional 10 weeks, for a total combined dosing duration of 12 weeks at the individual patient's established therapeutic dose [i.e., the last 2 weeks during dose titration plus 10 weeks of open label treatment]. Patients will complete all procedures as described [Table 1-1](#), [Table 1-2](#), [Table 1-3](#). Patients who demonstrate at least 5 kg weight loss at the end of the Open Label Treatment Period (or 5% weight loss for patients with baseline body weight < 100 kg) will continue onto the long-term (1 year) extension period. It is planned that the individual patient's therapeutic dose, established during the initial period of dose titration, will continue throughout the study. In consenting patients, a 2- to 4-week period of active treatment withdrawal will be included during the 1-year extension.

Thus, pre-amendment patients will progress sequentially through the study as depicted in [Figure 1](#).

For post-amendment 9 patients, upon providing informed consent, patients will enter the Screening Period. During the Screening Period, patients will be assessed for eligibility and complete all screening procedures as described in [Table 2](#). Each patient's genetic information will be reviewed by the Sponsor to confirm the patient is eligible for the study. During the Screening Period, each patient will be instructed to complete a hunger questionnaire on a daily basis and will be required to have completed at least four days of the questionnaire prior to first dose.

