Eligible patients will return to the clinic within 2 – 8 weeks of completing the Screening Visit for the Baseline Visit (Visit 2) and first dose of setmelanotide. Dose levels for all patients will escalate to a final dose of 3.0 mg/day during an initial dose-titration phase, but the starting dose will depend on patient age. Patients 6 up to 16 years old will initially be dosed at 1.0 mg/day for 2 weeks, beginning at the Baseline Visit on Study Day 1. Starting on Day 15, the dose will escalate to 2.0 mg/day and remain at that level for 2 weeks, until the patient returns to clinic for Visit 3 on Day 29. At Visit 3, the dose will be escalated to 3.0 mg/day; the patient will continue dosing at 3.0 mg/day for 12 weeks. Patients ≥16 years old will initiate dosing at 2.0 mg/day at the Baseline Visit, and continue dosing at that level for 2 weeks. The dose will be escalated to 3.0 mg/day beginning on Study Day 15, and the patient will continue that dose for 14 weeks. Study site staff will call all patients at their homes after the first 2 weeks of treatment to ensure the escalation occurred as planned and collect any adverse events (AEs).

Patients will continue dosing at 3.0 mg/day and return to the clinic every four weeks (Visits 3-5) to complete the assessments in [Table 2](#). After 16 weeks in the study, patients will return to the clinic for Visit 6. At Visit 6, the patient will receive the last setmelanotide injection.

Participation in the study will then conclude in one of the following two ways:

- Complete Visit 6 and enroll in a separate extension study, Rhythm Study RM-493-022. If RM-493-022 is not yet open at the clinic site, the patient will continue daily setmelanotide injections and other activities per the current study, as presented in the Schedule of Assessments (SOA) ([Table 2](#)). The patient will return to the clinic for Bridging Visits every 12 weeks for up to one year, until the extension study opens at the site. Additional clinic visits may be scheduled at the discretion of the primary investigator (PI).
- Decide not to participate in the extension study and proceed to the final study visit (Visit 7) in 4 weeks.

Patients on study prior to amendment 9 should transition to dose escalation as outlined in protocol amendment 9 in the manner outlined below:

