- 6 The Dose Titration phase will be a variable schedule lasting a minimum of 2 weeks in which patients will return to the clinic approximately every 2 weeks in order to establish the individual patient's therapeutic dose according to Protocol. Given the variable number of dose titration steps in the Dose Titration Phase, each Dose Titration Visit Number (V) will remain V2 with an alphabetized suffix added to each titration visit (i.e.; first dose titration at start of Week 1 = V2a, second dose titration at start of Week 3 = V2b, etc.). This will allow for the Visits to be appropriately tracked. Additionally, each dose titration visit will have the same pre and post dose assessments as outlined in the SOA (with the exception of Anti-Rm-493 antibodies, metabolic and hormonal assays, ECG, Inclusion/Exclusion review and Medical History Review).
- 7 Once the patient's individual therapeutic dose is established the patient will enter the Open Label Active Treatment phase for 10 additional weeks, for a combined total of 12 weeks of dosing at the therapeutic dose. During this time, the study calendar will be reset, starting when the therapeutic dose was initiated (i.e. the last 2 weeks of dose titration when the therapeutic dose was established). Therefore, the Open Label Active Treatment phase starts at the beginning of Week 3 (V2x – final dose titration visit). Patients losing 5 kg of weight (or 5% if baseline weight is < 100 kg) at the end of the Open Label Treatment phase will be eligible to enter the one-year extension.
- 8 During the titration period and the 10-week Open Label Treatment Period, patients (and/or parents/guardians) will measure blood pressure and heart rate at home once daily prior to dosing in the morning, and record the values. The measurements should be taken in triplicate and all 3 readings recorded. If needed, Rhythm will supply a blood pressure machine for these readings.

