- 9 Early Termination: For those patients who withdraw consent or are withdrawn and not willing to complete the remaining study visits, the early termination visit assessments should be performed, when possible. Final Visit: For patients who complete the study but do not wish to enroll into the future long-term extension study (as noted in Protocol Section 5.5), patients will be required to return for a Final Visit ~ 30 days after the last dose of setmelanotide, for a final follow-up safety assessment. Any ongoing AEs reported at this visit should be monitored as outlined in Protocol Section 7.4. For patients who enroll into the long-term extension study, this visit is not required. Additionally, patients who are not willing to return for the remaining clinic visits/Final Visit, assessments by home health care professionals can be arranged, or at a minimum, patients can be contacted via phone if amenable, to collect self-reported patient data (i.e.: weight, hunger, AEs, etc.).
- 10 [REDACTED]

11 Weight is to be measured at the clinic using the same scale after patients have emptied their bladder and while fasting. Patients are to wear light clothing or underwear, no shoes, and will be weighed at approximately the same time of day. Weight measurements are to be done in triplicate; waist circumference will be single measures.

12 Extra retain samples will consist of 2 serum and 2 plasma (K2EDTA) vacutainer tubes.

13 Study drug is administered by patients/caretakers beginning the morning of Day 1 and for the duration of dosing. Patients/caretakers will draw up and self-administer/administer the drug once on a daily basis in the morning. On days with clinic visits, the patients/caretakers will administer the drug in the clinic in the presence of the clinical staff to assure proper technique. Patients/caretakers will return all used vials to the clinic when they visit (the number recorded) and both clinic administered study drug, as well as outpatient study drug administration will be recorded in a study diary.

14 Injection site evaluations and scoring (by the clinical staff) will include identification and measurement of areas of erythema, edema and induration, as well as the presence of localized pain, tenderness and itching. Additional evaluation data can be collected at any visit where there are injection site reactions even if not a timepoint for formal assessment.

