To be collected on the first two, two-week dose titration visits (V2a and V2b). A blood sample will be obtained at Screening from all patients for genotyping for mechanisms considered to be possibly related to the safety or efficacy response to the study medication (e.g., other obesity related genes; drug metabolism). A portion of this sample may be used, under informed consent, for patients who do not have a diagnosis confirmed by genetic test to confirm diagnosis of one of the studied mutations prior to study participation. Global Hunger Questions will be administered in clinic as follows: Question 1 will be asked at screening, and Questions 1 and 2 will then be asked at Visit 6 (start of 52-week Open Label Extension), additional withdrawal Visits A, B, and C (see footnote 35), Visit 7, Visit 8 (~6 months) and Visit 14 (end of 1 year). Metabolic and Hormonal Assays: Assays will be collected and analyzed on an ongoing basis during or post study, including LH, FSH, TSH, free T4, ACTH (screening visit only)³⁶, IGF-1, and IGFBP-3, Serum procollagen type 1 N-propeptide, COOH-terminal telopeptide of type 1 collagen, N-terminal telopeptide of type 1 collagen, Bone-specific alkaline phosphatase, osteocalcin. Other assays (including testosterone, estradiol, GH, aldosterone, renin, cortisol and anti-inflammatory markers) will be measured on an as needed basis and would be assayed only if clinical signs or symptoms require further evaluation (e.g., renin and aldosterone would be measured only if BP increases are noted). Optional Withdrawal Visits A (start of withdrawal), B (after 2 weeks of withdrawal), and C (end of withdrawal). If it is determined a patient will participate in the optional withdrawal period, the 2 to 4 weeks off study drug will occur between visits 6 and 7 or between Visits 7 and 8 (first 13 weeks of 52-week extension). The following study assessments should be completed at these visits: Pregnancy test⁴, [REDACTED], Weight/Waist circumference¹¹, Injection site inspection¹⁴, Vital signs¹⁵, [REDACTED]³⁴ (both local and storage), [REDACTED], Adverse Event Assessment²⁵, Concomitant Meds Review, Telephone Contact, Serial Photographs³. If the patient only participates for 2 weeks, Visit C will not be completed and Visit B becomes the end of withdrawal visit. A sample for ACTH should be collected only at the Screening Visit and between 8 AM and 10 AM prior to study drug administration.

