- Body composition assessment may be performed using an appropriate method available at sites (e.g., BIA [REDACTED]). Refer to Protocol Section 11.11 for details.
- All BP and HR measurements are to be obtained in the sitting position following at least 5 minutes of rest. All measurements will be taken in triplicate, approximately 2 minutes apart. When possible, BP should be taken in the non-dominant arm throughout the study, using the same methodology (automated or manual). Body temperature (°C) and respiration rate (breaths/minute) will be obtained in the sitting position following at least 5 minutes of rest (Protocol Section 11.13).

9. A single 12-lead ECG will be performed in the supine position following a period of at least 10 minutes of rest (Protocol Section 11.14). At visit 2 the ECG will be performed before and 8 hours after dosing.
10. A urine pregnancy test may be performed to expedite availability of results prior to dosing on Day 1. All other pregnancy tests will be serum tests (Protocol Section 11.15); dosing may continue with results pending.

26. Patients/caretakers will draw up and self-administer/administer the drug once daily in the morning beginning the morning of Day 1 and for the duration of dosing. On days with clinic visits, the patients/caretakers will administer the drug in the clinic in the presence of the clinical staff to assure proper technique.
27. Patients/caretakers will return all (the number recorded) used vials to the clinic when they visit, and both clinic-administered study drug as well as outpatient study drug administration will be recorded in a study diary.
28. Adverse events will be recorded from the time a patient provides informed consent. AEs reported after dosing on Day 1 will be considered treatment-emergent AEs.
29. Patients who are <16 years of age will receive first daily dose of 3.0 mg at V3, at clinic site.
30. Study endpoints are analyzed at V6. After completing V6, patient enters a separate extension study (Protocol RM-493-022), does not enter the extension study and returns for the final study Visit 7 in 4 weeks, or completes Bridging Visits for up to one year or until the extension study is initiated.
31. Bridging Visits only needed if separate extension study RM-493-022 is not initiated at site at the time of V6.
32. Collected prior to study drug administration.

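### SAP 4.3.2 tabulates weight change as FAS at all visits, but pre-Amendment 9 patients reached the extension visits only by losing 5 kg or 5%, so the later means are selected on the outcome; V7 also means on drug in one schedule and off drug in the other

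*SAP*

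**What the plan says.** **The table.** SAP 4.3.2 plans descriptive statistics for weight that "will be presented for patients of the FAS for all visits by subgroup of RGDO and overall". Under SAP 2.1 the FAS needs one dose and a baseline weight (certain sites excluded); there is no condition on response. SAP 3.10 makes no general substitution for missing values. SAP 3.2 reports N with each mean.

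**The gate.** For patients enrolled before Amendment 9, SAP 1.3.1 says "Patients who demonstrate at least 5 kg weight loss at the end of the Open Label Treatment Period" (or 5% if baseline weight is below 100 kg) go on to the one-year extension. Footnote 7 to the pre-Amendment 9 schedule repeats the threshold: patients who meet it "at the end of the Open Label Treatment phase will be eligible to enter the one-year extension". The extension visits are V7 to V14 (Table 1-3), with weight measured at each.

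**Two V7 visits.** In Table 1-3, V7 is Week 20, Day 141, with study treatment marked as given. Its day count is not from first dose, because "the study calendar will be reset, starting when the therapeutic dose was initiated". In Table 2 (Amendment 9), V7 is also Week 20, Day 141, but it is the end-of-study visit for a patient who "does not enter the extension study and returns for the final study Visit 7 in 4 weeks", the last injection having been given at V6. SAP 3.11 tabulates by the visit recorded on the CRF. It sends the mapping of pre-Amendment 9 patients who finish before their visits are updated to a separate document.

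**The concern.** The variable that decides who enters the extension is the variable being averaged. A row described as FAS at Week 26 or Week 52 invites comparison with the FAS rows before it. For gated patients that comparison is unfair: those who lost too little have left the row by rule, so the mean can fall although no patient's expected weight has changed. N falls too, but N alone does not say that the missing patients were removed for insufficient loss.

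V7 adds a second ambiguity. If values from the two schedules are pooled under one label, the row mixes responders on drug with patients four weeks off drug who chose not to continue. Some pre-Amendment 9 V7 values may also follow a drug holiday, since "the 2 to 4 weeks off study drug will occur between visits 6 and 7 or between Visits 7 and 8".

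At stake are the long-term rows of a descriptive secondary table. In an exploratory study, summaries of this kind are the main output, and SAP 3.12 foresees data cuts for business decisions or a regulatory submission.

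**Working it through.** The plan gives no figure to reproduce. The check has two parts.

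**1. Gate effect (illustration; inputs assumed, not in the documents)**

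- Percent change at ~3 months and at a later visit: bivariate normal, same mean *m* and SD *s* at both times (no true change), correlation ρ = 0.5 to 0.8.
- Baseline weight: Normal, mean 120 kg, SD 30 kg.
- Gate from the SAP: 5% loss below 100 kg, otherwise 5 kg.

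For a fixed weight the excess has a closed form. With gate *g*% and a = (−g − m)/s, the pass rate is Φ(a) and the excess loss at the later visit is ρ·s·φ(a)/Φ(a). At 120 kg, g = 100 × 5/120 = 4.17. With m = −5, s = 6: a = (−4.17 + 5)/6 = 0.139, Φ(a) = 0.555, φ(a)/Φ(a) = 0.712. The excess is 0.5 × 6 × 0.712 = 2.1 points at ρ = 0.5, and 0.8 × 6 × 0.712 = 3.4 at ρ = 0.8.

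Simulation over the weight distribution (2,000,000 draws per case):

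| True mean (SD) | Pass gate | Later mean in passers, ρ 0.5 to 0.8 | Excess loss (points) |
|---|---|---|---|
| −3% (5) | 41% | −5.35 to −6.76 | 2.3 to 3.8 |
| −5% (6) | 56% | −7.12 to −8.38 | 2.1 to 3.4 |
| −10% (6) | 83% | −10.89 to −11.43 | 0.9 to 1.4 |

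Other inputs move the range. With means of −2, −5 or −8%, SD 4 or 6 and ρ of 0.7 or 0.9, a plain 5% gate gives 1.1 to 6.2 points; at a fixed 150 kg (gate 3.33%) it gives 0.6 to 5.1.

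*Dilution.* Let f be the gated share, P the pass rate, E the later mean in passers, and r the share of ungated patients still on treatment and observed. Then row mean = [f·P·E + (1−f)·r·m] / [f·P + (1−f)·r]. For m = −5, ρ = 0.8, f = 0.5, r = 1: (0.278 × −8.38 + 0.5 × −5)/0.778 = −6.21, an excess of 1.2 points. Across f = 0.25 to 0.75 and all three cases the excess is 0.2 to 2.1 points if r = 1, and 0.4 to 3.0 if r = 0.3.

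**2. V7 side by side**

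| | Pre-Amendment 9 V7 | Amendment 9 V7 |
|---|---|---|
| Label | Week 20, Day 141 | Week 20, Day 141 |
| Clock starts | first therapeutic dose (reset) | first dose |
| Treatment | on drug, possibly soon after a withdrawal | off drug, 141 − 113 = 28 days after V6 |
| Who is there | met the 5 kg / 5% rule | chose not to continue |

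If the two were pooled, the result would depend on the mix. With assumed means of −9% (gated, on drug) and −3% (off drug), a row of 10 with 2, 5 or 8 on-drug patients averages (2 × −9 + 8 × −3)/10 = −4.2%, −6.0% or −7.8%.

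Even the direction of error is open. Apply the dilution formula with m = −3, P = 0.41, E = −6.05 (ρ = 0.65) and an assumed regain added to the ungated mean. With f = 0.75, r = 0.1 and no regain, the row is −5.82, which is 2.8 points too much loss. With f = 0.25, r = 0.5 and 5 points of regain, the row is +0.27, which is 3.3 points too little.

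**The case against.** - **FAS is not a false label.** It requires a dose and a baseline weight, and observed-case means by visit with N shown are ordinary practice. That stands. The defect is that the row does not say who remains and why.
- **The Protocol already limits the long-term analyses.** Section 13.4 describes 1-year weight as being in those who continue past 3 months, and 13.5 calls analyses of extension patients supplemental. This is a real mitigation, but SAP 4.3.2 does not carry the restriction over.
- **Endpoints are analysed at V6** (Table 2, footnote 30). This supports reading later rows as follow-up, yet 4.3.2 asks for all visits.
- **Old data may go only to listings** (SAP 3.2). That rule covers data no longer collected. Weight still is, so it does not clearly remove V8 to V14, though it leaves some doubt that those rows will be produced.
- **Disposition (SAP 4.1) counts patients before and after Amendment 9 and gives withdrawal reasons.** Useful, but not by visit, and it need not identify patients who missed the threshold.
- **The gated group may be small.** Pre-Amendment 9 patients past 16 weeks could move to the extension study or Bridging Visits with no weight condition stated (SAP 1.3.1). This stands and leaves the overall size unknown.

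Two stronger readings are tempting. A reader might infer that on-drug and off-drug V7 values will be pooled. The documents show only that they share a label under a rule that tabulates by label; the mapping document was not available and text after 4.3.2 is blacked out. A reader might also infer that the main efficacy result is biased. It is not: SAP 4.3.1 uses a 60 to 120 day window with the last earlier observation as fallback, and does not draw on the extension-visit means.

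**Conclusion.** The point holds in limited form. Followed as written, SAP 4.3.2 yields later weight means that, for patients who came through the old rule, are selected on weight loss and tend to overstate loss for the full FAS. This is a documented rule, not ordinary dropout. The size cannot be computed from the documents. Under the main assumptions it is about 0.9 to 3.8 points in gated patients alone and 0.2 to 3.0 points after dilution. These figures rest on assumed means, SDs, correlations, baseline weights and gated share, none of which the plan gives. The double meaning of V7 is a fact; a pooled V7 row is only a possibility. The ~3-month responder endpoint and the ~3-month weight summary are unaffected. Severity is minor to moderate, confined to descriptive secondary rows.

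**What to change.** In SAP 4.3.2:

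1. Restrict the FAS by-visit weight table to visits up to the ~3-month endpoint (V6 for Amendment 9 patients).
2. Show later on-treatment visits, both pre-Amendment 9 extension visits and Bridging Visits, in one summary titled *patients who continued*, in line with Protocol 13.4 and 13.5. Give n continuing out of N in the FAS, with the same patients' ~3-month change beside the later change. Footnote the 5 kg / 5% rule, the number of pre-Amendment 9 patients who did not meet it, and their ~3-month mean.
3. State that Amendment 9 V7 weights (patients who "Decide not to participate in the extension study and proceed to the final study visit (Visit 7) in 4 weeks") are tabulated as off-treatment follow-up and not pooled with pre-Amendment 9 V7. Keep withdrawal-period weights, and weights from the visit at which "patients will be required to return for a Final Visit ~ 30 days after the last dose of setmelanotide", out of the on-treatment rows.

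Cost: SAP wording, one continuers' summary, a separate off-treatment display and footnotes; no new data. Downsides: small cells in subgroups of 1 to 15 patients, less favourable long-term figures, and some apparent regain from ~3 months in gated patients through regression to the mean (about 0.4 to 2.3 points under the main assumptions). The ~3-month and later changes therefore need to stand side by side.
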